## For Patients with Non-Measurable Disease (i.e., Non-Target Disease)

## MEMORIAL SLOAN-KETTERING CANCER CENTER

IRB#: 14-211 A (7)

APPROVED: 19 DEC 2016

Non-Target Lesions	New Lesions	Overall Response
CR	No	CR
Non-CR/non-PD	No	Non-CR/non-PD*
Not all evaluated	No	not evaluated
Unequivocal PD	Yes or No	PD
Any	Yes	PD

\* 'Non-CR/non-PD' is preferred over 'stable disease' for non-target disease since SD is increasingly used as an endpoint for assessment of efficacy in some trials so to assign this category when no lesions can be measured is not advised

#### 12.1.5 Duration of Response

Duration of overall response: The duration of overall response is measured from the time measurement criteria are met for CR or PR (whichever is first recorded) until the first date that recurrent or progressive disease is objectively documented (taking as reference for progressive disease the smallest measurements recorded since the treatment started).

The duration of overall CR is measured from the time measurement criteria are first met for CR until the first date that progressive disease is objectively documented.

Duration of stable disease: Stable disease is measured from the start of the treatment until the criteria for progression are met, taking as reference the smallest measurements recorded since the treatment started, including the baseline measurements.

#### 12.1.6 Progression-Free Survival

PFS is defined as the duration of time from start of treatment to time of progression or death, whichever occurs first.

### 13.0 CRITERIA FOR REMOVAL FROM STUDY

Any patient who experiences toxicity requiring ribavirin dose reduction below "dose level minus 3" (See Section 11.1) will be removed from study.

Any subject who requires treatment delay of more than 21 days in a given cycle will be removed from study.

If at any time the patient develops progressive disease, he/she will be taken off study.

Patients may be removed from the study for protocol non-compliance.

If at any time the patient develops unacceptable toxicity, he/she will be removed from study.

## MEMORIAL SLOAN-KETTERING CANCER CENTER

IRB#: 14-211 A (7)

APPROVED: 19 DEC 2016

Participants can be removed from the study at any time if the study doctor feels that it is in their best interest to do so.

### 14.0 BIOSTATISTICS

A sample size of 12 patients will be accrued and followed until progression of disease (or until removal of study for other medical/logistical reasons), in this pilot study with the objective to obtain preliminary evidence of efficacy in the selected patient population of R/M HPV related malignancies. Radiographic responses, determined by RECIST 1.1 criteria, will be tabulated by adding partial responses and complete responses (CR + PR). The best response for each patient during the study will be used.

Efficacy considerations for the statistical design of this study are informed by historical data regarding second-line or greater systemic therapy for patients with recurrent/metastatic (R/M) head and neck cancer, cervical cancer, or anal cancer. Among patients with R/M head and neck cancer, the historical estimate for objective response rate with palliative chemotherapy after first line is 15% [39, 40]. Similarly, the response rate of palliative single agent chemotherapy for advanced cervical cancer is approximately 15-20% [41, 42]. For R/M anal cancer, no regimen has been shown to be effective after first line platinum + 5-fluorouracil [43].

The regimen would be considered worthy of further study if radiographic responses are observed in at least 2 of 12 subjects. The probability of missing an effect (observing 0 or 1 responses out of 12 patients if the true response rate is 30%), is 0.09. Overall Survival and Progression-Free Survival will be estimated with the Kaplan-Meier method.

Tissue correlative studies will be for purposes of hypothesis generation. We will explore if the anti-Gli-1 IHC score (scale 0-3 dichotomized to low/high) is related to response (CR+PR) using Chi-square or Fisher's exact test. The following provisional scoring system will be used (% refers to percentage of tumor cells that stain positively [cytoplasm and/or nucleus] for Gli 1):

IHC score 0: <=5%

IHC score 1: >5 and <=30%

IHC score 2: >30% and <=50%

IHC score 3: >50%

Additionally, baseline and post-progression Gli-1 expression will be reported (using this provisional scoring system) among the patients who have an initial radiographic response and a post-progression biopsy.

The number and grade of toxicities will be tabulated using NCI CTCAE version 4, as well as the number of dose reductions in all cycles.

The projected accrual rate is 1 to 2 patients per month.

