## 2.0 OBJECTIVES AND SCIENTIFIC AIMS

Primary Objective: To obtain a preliminary efficacy assessment for ribavirin monotherapy among patients with R/M HPV-related malignancies

Secondary Objectives:

- (1) To describe overall survival and progression-free survival;
- (2) To describe the safety and tolerability of ribavirin in this patient population
- (3) To explore Gli-1 expression, as detected by immunohistochemistry (IHC) in pre-treatment archived pathology samples, as a candidate biomarker for efficacy of ribavirin in these cancers;
- (4) Among subjects who initially respond to ribavirin, to explore if subsequent acquired resistance is associated with increased Gli-1 expression.

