## 9.0 TREATMENT/INTERVENTION PLAN

### 9.1 Clinical Plan

Study subjects will self-administer ribavirin 1400 mg PO BID (total dose, 2800 mg/day).

Ribavirin should be taken with food, not in a fasting condition.

All patients will complete pill diaries to document administration of study drug. Patients should be instructed to bring completed pill diaries and all pill bottles to each visit.

Cycle length is 28 days with continuous dosing. Clinic visits for safety assessments and routine laboratory studies will occur weekly in Cycle 1, in weeks 1 and 3 of Cycle 2, and on Week 1 of subsequent cycles ( $\pm$  3 days). Although clinic visits and lab tests should generally occur on the same day each week to facilitate continuity with providers, there is no requirement regarding the day of the week of these visits.

Toxicities will be graded according to NCI CTCAE version 4.

Cross sectional imaging (CT or MRI) is obtained at baseline and q2 cycles. Imaging scans will be scheduled to occur in the last week ( $\pm$  2 days) of each even-numbered cycle. However, after completion of cycle 4, the interval between scans may be increased to q3 cycles, at the discretion of the investigator.

Response assessments will follow RECIST 1.1 criteria (See Section 12).

Patients may remain on study until disease progression or unacceptable toxicity. There will be a post-treatment visit 30 days ( $\pm$  7 days) from last dose of drug for patients who maintain active follow up. If a patient is unable to attend the post-treatment visit due to medical or logistical issues or lost to follow-up, this will not be a protocol violation.

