### 9.2 Immunohistochemistry (IHC)

Anti Gli-1 antibody (Glioma associated oncogene 1; H-300 rabbit polyclonal, Santa Cruz Biotechnology, sc-20687) has been used extensively for IHC in studies of cervix cancer and head and neck cancer [35, 36] and will be optimized for IHC in our Pathology Core. Formalin-fixed paraffin-embedded (FFPE) slides will be prepared in the Department of Pathology according to standard practices, and will be analyzed by [name]. Archived FFPE pre-treatment tumor samples will be processed for IHC detection of Gli-1 and scored by the study pathologist (scale 0-3 dichotomized to low/high).

For any patients who initially experience a radiographic response to ribavirin by RECIST 1.1 (confirmed or unconfirmed), at time of subsequent disease progression a research tumor biopsy will be obtained (unless such biopsy is deemed to pose unacceptable safety risk). Gli-1 expression will be assessed by IHC, in an effort to explore if increased Gli-1 expression (compared with pre-treatment tissue) may be associated with acquired resistance to ribavirin in patients with HPV-related malignancies. These post-treatment biopsies should generally be obtained within 2 weeks of the last dose of ribavirin, although it will not be considered a violation if the biopsy occurs outside of this time window. The gauge of the needle will be at the discretion of the interventional radiologist, although 18 gauge is preferred.

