## 10.0 EVALUATION DURING TREATMENT/INTERVENTION.

		Cycle 1	Cycle 2	Cycle ≥3	Post Treatment d
	Baseline	Weeks 1, 2, 3 and 4	Weeks 1 and 3	Week 1	
History and Physical	X	X	X	X	X
CBC, Comp panel	X	X	X	X	X
PT/aPTT	X				
Serum Pregnancy Test	X				
EKG a	X				
Radiologic Assessment (CT or MRI) b	X		X	X	
Archival Tissue	X				
Research biopsy c					X c
Adverse Event and Concomitant Medications Monitoring		Continuous Monitoring for Adverse Events			
Ribavirin		Continuous BID dosing			

a Baseline EKGs to be performed within 8 weeks prior to treatment

b Radiologic assessments occur at baseline (within 4 weeks of starting treatment) and q2 cycles. Imaging scans will be scheduled to occur in the last week ( $\pm$  2 days) of each even-numbered cycle. However, after completion of cycle 4, the interval between scans may be increased to q3 cycles, at the discretion of the investigator.

c Research biopsy at time of progression of disease is only for patients who experience initial radiographic response. When done, every effort should be made to obtain the research biopsy within 2 weeks of the last dose of ribavirin.

d The post treatment evaluation should occur 30 days ( $\pm$  1 week) after the last dose of ribavirin, for patients who maintain active follow up. The one exception is the post-treatment biopsy for patients who had previously responded (see footnote b)

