## MEMORIAL SLOAN-KETTERING CANCER CENTER

IRB#: 14-211 A (7)

APPROVED: 19 DEC 2016

- A persistent or significant incapacity or substantial disruption of the ability to conduct normal life functions
- A congenital anomaly/birth defect
- Important Medical Events (IME) that may not result in death, be life threatening, or require hospitalization may be considered serious when, based upon medical judgment, they may jeopardize the patient or subject and may require medical or surgical intervention to prevent one of the outcomes listed in this definition

**Note:** Hospital admission for a planned procedure/disease treatment is not considered an SAE.

SAE reporting is required as soon as the participant signs consent. SAE reporting is required for 30-days after the participant's last investigational treatment or intervention. Any events that occur after the 30-day period and that are at least possibly related to protocol treatment must be reported.

If an SAE requires submission to the IRB office per IRB SOP RR-408 'Reporting of Serious Adverse Events', the SAE report must be sent to the IRB within 5 calendar days of the event. The IRB requires a Clinical Research Database (CRDB) SAE report be submitted electronically to the SAE Office as follows:

Reports that include a Grade 5 SAE should be sent to [[contact]](mailto:[contact]). All other reports should be sent to [[contact]](mailto:[contact]).

The report should contain the following information:

Fields populated from CRDB:

- Subject's initials
- Medical record number
- Disease/histology (if applicable)
- Protocol number and title

Data needing to be entered:

- The date the adverse event occurred
- The adverse event
- The grade of the event
- Relationship of the adverse event to the treatment (drug, device, or intervention)
- If the AE was expected
- The severity of the AE
- The intervention
- Detailed text that includes the following
  - A explanation of how the AE was handled
  - A description of the subject's condition
  - Indication if the subject remains on the study
- If an amendment will need to be made to the protocol and/or consent form
- If the SAE is an Unanticipated Problem

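### Overall survival is a secondary Kaplan-Meier outcome, but the visible plan has no survival follow-up beyond about 30 days after the last dose, and no definition or censoring rule for it

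*Combined protocol and SAP*

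**What the plan says.** **Objective and method.** Section 2.0 lists as a secondary objective "To describe overall survival and progression-free survival". Section 14.0 adds: "Overall Survival and Progression-Free Survival will be estimated with the Kaplan-Meier method".

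**Length of follow-up.** Section 14.0: "A sample size of 12 patients will be accrued and followed until progression of disease", or until removal for other medical or logistical reasons. Section 13.0: "If at any time the patient develops progressive disease, he/she will be taken off study".

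**What continues after that.**
- One visit. Section 10.0, footnote d: "The post treatment evaluation should occur 30 days" (with a one-week window) after the last dose, for patients still in active follow-up. Under Section 9.1, if a patient cannot attend or is "lost to follow-up, this will not be a protocol violation".
- A biopsy, in patients with an earlier radiographic response only. Section 9.2: "at time of subsequent disease progression a research tumor biopsy will be obtained".
- Serious adverse events, which include death. Section 17.3: "SAE reporting is required for 30-days after" the last treatment or intervention. Later events are reported only if at least possibly related to treatment.

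**What is defined.** Section 12.1.6 defines progression-free survival (PFS) by start point and event. OS has no counterpart in the visible text, and no OS censoring rule, vital-status schedule or data cut-off is given.

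**The concern.** OS needs deaths and last-known-alive dates for every patient, whatever happened to treatment. As written, planned observation largely stops at progression, the event that usually marks a change in the risk of death. A death from cancer alone more than 30 days after the last dose falls outside the SAE window, and no scheduled contact would find it.

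Kaplan-Meier assumes that patients censored at a given time have the same later risk of death as those still under observation. Censoring triggered by progression breaks that assumption. The curve would rest mainly on deaths before progression or shortly after it, and could mislead anyone using it as a reference when planning a later study. The absence of a censoring rule adds a second problem: two analysts could build different OS curves from the same 12 patients.

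**Working it through.** **1. The plan's own figure.** Section 14.0 gives 0.09 as the probability of 0 or 1 responses in 12 at a true response rate of 30%.

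P(0 or 1) = 0.7^12 + 12 × 0.3 × 0.7^11 = 0.0138 + 0.0712 = 0.085, which rounds to 0.09. It reproduces and does not involve OS.

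**2. Inputs.** From the documents: 12 patients; scans every two 28-day cycles (56 days); last scheduled contact and SAE window 30 days after the last dose. Assumed, because the documents give no survival figures: median time to first event (progression or death), median survival after progression (m, months), the share of patients dying without documented progression (q), and a last dose at detected progression.

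**3. Hand calculation.** Ignore scan delay, let recording stop one month after progression, and take a constant hazard:

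share of deaths seen = q + (1 − q) × (1 − 0.5^(1/m))

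| q | m = 1 | m = 2 | m = 4 | m = 9 |
|---|---|---|---|---|
| 0 | 50% | 29% | 16% | 7% |
| 10% | 55% | 36% | 24% | 17% |
| 25% | 63% | 47% | 37% | 31% |

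For example, q = 10% and m = 4 gives 0.10 + 0.90 × 0.159 = 0.243, or about 2.9 of 12 deaths.

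**4. Simulation with scan timing.** Progression is dated to the next 56-day scan and OS follow-up ends 30 days later. Times are exponential. Median time to first event is 2, 3 or 4 months and q runs from 5% to 30% in steps of 5 points. Bias is Kaplan-Meier minus true 12-month OS; within 0.005 of zero counts as none.

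| Post-progression survival | Scenarios | Deaths seen | Bias at 12 months | Up / down |
|---|---|---|---|---|
| Median 3-12 months, constant hazard | 108 | 15-56% | −0.07 to +0.21 | 101 / 5 |
| Median 1-2 months, constant hazard | 36 | 51-81% | +0.03 to +0.18 | 36 / 0 |
| Median 3-12 months, falling hazard (Weibull shape 0.6) | 108 | 25-59% | −0.13 to +0.08 | 47 / 53 |

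Worked case (3 months to first event, m = 5, q = 10%): 31% of deaths seen; Kaplan-Meier 12-month OS 0.513 against a true 0.348, a bias of +0.165.

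**5. Why the direction varies.** With constant hazards, the death hazard before progression is q × ln 2 / (median time to first event), and after it ln 2 / m.
- Worked case: 0.10 × 0.693 / 3 = 0.023 per month before, 0.693 / 5 = 0.139 after. The unobserved time carries the higher risk, so the curve is too high.
- Opposite case (2 months, m = 12, q = 30%): 0.30 × 0.693 / 2 = 0.104 before, 0.693 / 12 = 0.058 after. The curve is too low, by about 0.07.
- With a falling hazard, the month that is observed after progression is the riskiest one, which also pulls the curve down.

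Removal for toxicity and the optional three-cycle scan interval are not modelled.

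**The case against.** **Deaths may be recorded anyway.** Nothing forbids collecting vital status. Off study does not end all data collection here, since the 30-day visit, the responder biopsy and SAE reporting can follow it. Section 16.2 has follow-up monitored periodically, and Section 18.1 says the consent form will state the likely follow-up. The consent pages were not available for review. All this stands, and it makes a cut-off about a month after progression the natural reading and not a written rule. None of these passages supplies a survival schedule, though, and without one ascertainment depends on who happens to stay in contact.

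**Size and direction.** A reader might infer that more than half of deaths will be missed and that the OS curve will be too high. The documents do not support either statement, because they give no PFS or OS figure. In the exponential scenarios with medians of 3 to 12 months, fewer than half of deaths are seen in about 100 of 108. That counts chosen scenarios and is not a probability. It fails in all 36 scenarios with medians of 1 to 2 months, and the upward direction fails in more than half of those with a steeply falling hazard.

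**Weight.** OS is only to be described. With complete follow-up of 12 patients, the standard error at a 12-month OS of 0.35 is √(0.35 × 0.65 / 12) = 0.14, so the worked bias of 0.165 is little more than one standard error. This is fair and lowers the severity. It does not justify leaving OS undefined, since a systematic error is not described by a confidence interval.

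**Conclusion.** The point holds as a minor one. The visible plan promises a Kaplan-Meier OS estimate but gives no OS definition or censoring rule, and no vital-status follow-up beyond about 30 days after the last dose. Followed on the natural reading, it would leave many later deaths unrecorded and censor patients soon after progression. That is informative censoring, and the OS curve would be unreliable.

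How many deaths would be lost, and which way the curve would err, cannot be settled from the documents. The simulated ranges rest wholly on assumed survival times, hazard shapes and one reading of when contact ends. The absence of survival follow-up is established for the visible text only. No decision depends on OS: the requirement of at least 2 responses in 12, and its stated 0.09, are untouched.

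**What to change.** In Sections 9.1, 10.0, 13.0 and 14.0, separate end of treatment from end of data collection, without changing when treatment stops. Then:
- define OS as the time from start of treatment to death from any cause, censored at the last date known alive;
- after treatment ends for any reason, record vital status by chart review or telephone, for example every 3 months, until death or a fixed cut-off date stated in Section 14.0.

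If survival follow-up is not wanted, delete OS from Sections 2.0 and 14.0 so that objective and plan agree.

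The cost is a short amendment and a few chart or telephone checks on 12 patients at one centre. The Research Study Assistant already assigned under Section 16.1 could do them. The downside is a little extra data collection and later final data.

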## 6.1 CRITERIA FOR SUBJECT ELIGIBILITY

### 6.2 Subject Inclusion Criteria

1. Recurrent and/or metastatic HPV-related carcinoma of the cervix, anus, vagina, vulva, penis, or oropharynx. The cancer diagnosis must be confirmed by slide review in the MSKCC Department of Pathology. HPV positive status must be demonstrated by HPV in situ-hybridization (ISH) and/or by p16 immunohistochemistry (IHC).  
Note: For cervix squamous cancer, HPV ISH test or p16 IHC test is not required, because all cervix squamous cancers are presumed to be HPV-associated.
2. Adults ( $\geq$  18 years of age)
3. ECOG performance status of 1 or better
4. Measurable disease according to RECIST 1.1 criteria
5. Availability of archived tumor tissue for correlative studies (5 unstained slides)
6. Adequate organ function, as follows:
  - Adequate bone marrow reserve: absolute neutrophil count (ANC)  $\geq$  1.5  $\times$  10^9/L, platelets  $\geq$  160  $\times$  10^9/L, hemoglobin  $\geq$  10 g/dL
  - Hepatic: total bilirubin within ULN (upper limit of normal); alkaline phosphatase (AP), aspartate transaminase (AST) and alanine transaminase (ALT)  $\leq$  2.0  $\times$  ULN
  - Renal: Serum creatinine  $\leq$  1.3 mg/dL. Patients with serum creatinine  $>$  1.3 mg/dL may be eligible if creatinine clearance (CrCl)  $\geq$  55 mL/min based on the standard Cockroft and Gault formula.
7. Ability to swallow oral medication.
8. Patients of childbearing potential must have a negative serum pregnancy test within 14 days of treatment. Patients must agree to use a reliable method of birth control during and for 6 months following the last dose of study drug.
9. At least one prior systemic therapy regimen for R/M HPV-related carcinoma

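### Does the 2-of-12 rule in Section 14 need its chance of passing at the cited historical rates, and a confidence interval, written into the plan?

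*Combined protocol and SAP*

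**What the plan says.** All the design statistics are in Section 14.0 (Biostatistics). The size is fixed: "A sample size of 12 patients will be accrued and followed until progression of disease". Complete and partial responses are added and tabulated, using each patient's best response. The decision rule is "The regimen would be considered worthy of further study if radiographic responses are observed in at least 2 of 12 subjects". The only operating characteristic is the probability of "observing 0 or 1 responses out of 12 patients if the true response rate is 30%), is 0.09".

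The section says that historical results inform the design. For head and neck cancer, "the historical estimate for objective response rate with palliative chemotherapy after first line is 15" percent. For cervical cancer, the "response rate of palliative single agent chemotherapy for advanced cervical cancer is approximately 15-20" percent. For anal cancer, "no regimen has been shown to be effective after first line platinum + 5-fluorouracil". None of these is named as a null or uninteresting rate.

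Section 2.0 words the primary objective modestly: "To obtain a preliminary efficacy assessment for ribavirin monotherapy among patients with R/M HPV-related malignancies". Sections 1.0 and 4.2 call the trial a pilot. Section 6.2 admits "HPV-related carcinoma of the cervix, anus, vagina, vulva, penis, or oropharynx" and states no quota by site.

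Section 14.0 names Kaplan-Meier estimation for survival and progression-free survival, and a chi-square or Fisher's exact test for the Gli-1 score. It names no interval for the response rate.

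**The concern.** A rule with a cut-off has two sides, and Section 14.0 quantifies one. A reader sees a 9% risk of discarding a good drug but not how easily a drug no better than the cited chemotherapy would pass. The cut-off, 2/12 = 16.7%, lies within the 15-20% that the section quotes, so such a drug would pass more often than not. Without a planned interval, a bare pass on two responses could be taken for more than it shows. At stake is how a pass is read when further work is considered, including the combination with a PI3K inhibitor foreseen in Section 3.0.

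**Working it through.** **Inputs.** From Section 14.0: n = 12, pass if X ≥ 2, target rate 30%, stated miss risk 0.09, historical rates 15% and 15-20%. The 5% rate and the site mixes below are assumptions, not document figures.

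**1. The plan's own figure.** With X ~ Binomial(12, p), P(X ≤ 1) = (1−p)^12 + 12p(1−p)^11. At p = 0.30 this is 0.0138 + 0.0712 = 0.0850, which rounds to the stated 0.09.

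**2. Chance of passing if all 12 patients share one rate**, P(X ≥ 2) = 1 − P(X ≤ 1):

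| True rate | P(pass) |
|---|---|
| 5% | 1 − 0.8816 = 0.118 |
| 15% | 1 − 0.4435 = 0.557 |
| 20% | 1 − 0.2749 = 0.725 |
| 30% | 1 − 0.0850 = 0.915 |

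**3. Mixed sites.** Four of the six eligible sites have no numeric benchmark in Section 14.0. Assume that 4 to 6 of the 12 patients come from them with a 5% background rate and the rest have 15% or 20%. Summing the two binomials gives P(pass) between 0.34 and 0.56. Varying the assumed 5% from 0% to 10% widens this to 0.22 to 0.62. So 0.56-0.73 is the upper end of the plausible range. Section 6.2 also sets no upper limit on prior regimens, and heavily pretreated patients could lower it further.

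**4. What a pass or fail tells us** (likelihood ratios):

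- Pass, 30% against 15%: 0.9150/0.5565 = 1.64.
- Pass, 30% against 20%: 0.9150/0.7251 = 1.26.
- Pass, 30% against 5%: 0.9150/0.1184 = 7.7.
- Fail, 15% against 30%: 0.4435/0.0850 = 5.2.
- Fail, 20% against 30%: 0.2749/0.0850 = 3.2.

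A pass is therefore weak evidence against the historical rates and fairly strong evidence against near-inactivity. A fail is informative.

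**5. A pass is not one result.** Probability of each exact count:

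| Responses | at 15% | at 20% | at 30% |
|---|---|---|---|
| 2 | 0.292 | 0.283 | 0.168 |
| 3 | 0.172 | 0.236 | 0.240 |

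Exactly 2/12 favours 15% over 30% by 0.292/0.168 = 1.74, and 20% over 30% by 1.69. At 3/12 the direction changes: 30% is favoured over 15% by 0.240/0.172 = 1.4, and is level with 20%. At a true 30%, three or more responses have probability 0.75. Exact (Clopper-Pearson) 95% intervals are 2.1% to 48.4% for 2/12, 5.5% to 57.2% for 3/12 and 15.2% to 72.3% for 5/12. Five or more responses have probability 0.024 at a true 15%.

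**6. Would another cut-off do better?** Passing at 3 or more gives 0.264 at 15% and 0.442 at 20%, but raises the miss risk at 30% to 1 − 0.747 = 0.253. Passing at 4 or more gives 0.092 and 0.205, with a miss risk of 1 − 0.507 = 0.493. With 12 patients, no cut-off is good on both sides.

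**The case for a change.** The strongest case for a change is that the protocol itself chose a formal cut-off, a target rate and a quantified error, and itself invoked the historical rates. Having given one side of the rule, it should give the other. Three sentences would do it, at no cost in patients and with no change of threshold: the chance of passing at 5%, 15% and 20%, an exact interval, and a caution on what a pass means.

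The facts in this stand. The probabilities are right, the section is silent on them, and a result of exactly 2/12 cannot separate ribavirin from chemotherapy at 15-20%. The inference that the plan is defective does not stand. The rule asks whether to study the drug further, not whether it beats chemotherapy. Section 3.0 looks ahead to combinations, where an oral agent matching 15-20% could reasonably go forward. Passing such a drug is then not an error.

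A blanket caution that a pass is no evidence of activity at or above historical therapy would be wrong. A pass includes 5/12, whose interval starts at 15.2%, and the likelihood ratios for a pass (1.64 and 1.26) exceed 1. The caution holds only for the minimum passing result.

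**Conclusion.** No change to the plan is needed. The stated 0.09 is correct. What is missing is descriptive: a chance of passing of 0.12 at 5%, 0.56 at 15% and 0.73 at 20% with all patients at one rate, and lower if some sites or later-line patients respond less often. These are not false-positive rates, because the protocol sets no null. A low bar suits a 12-patient pilot meant to avoid dropping an active drug, and raising it to three would nearly triple the miss risk at 30% (0.253/0.085 = 3.0).

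The probabilities follow from n, the cut-off and the rates already printed. The exact interval needs only the final count and can go in the report without an amendment. The point to carry into that report is narrow: if exactly two patients respond, the interval of 2.1% to 48.4% contains both the cited 15-20% and the 30% target, and the result should be read so.

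This conclusion rests on reading the rule as a screen for further study, as the protocol's wording supports. It would differ if the protocol claimed superiority to historical therapy, which it does not.

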**Target lesions.** All measurable lesions up to a maximum of 2 lesions per organ and 5 lesions in total, representative of all involved organs, should be identified as **target lesions** and recorded and measured at baseline. Target lesions should be selected on the basis of their size (lesions with the longest diameter), be representative of all involved organs, but in addition should be those that lend themselves to reproducible repeated measurements. It may be the case that, on occasion, the largest lesion does not lend itself to reproducible measurement in which circumstance the next largest lesion which can be measured reproducibly should be selected. A sum of the diameters (longest for non-nodal lesions, short axis for nodal lesions) for all target lesions will be calculated and reported as the baseline sum diameters. If lymph nodes are to be included in the sum, then only the short axis is added into the sum. The baseline sum diameters will be used as reference to further characterize any objective tumor regression in the measurable dimension of the disease.

**Non-target lesions.** All other lesions (or sites of disease) including any measurable lesions over and above the 5 target lesions should be identified as **non-target lesions** and should also be recorded at baseline. Measurements of these lesions are not required, but the presence, absence, or in rare cases unequivocal progression of each should be noted throughout follow-up.

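### Pre-treatment Gli-1 is set against efficacy only as low/high by CR+PR yes/no, which is very unlikely to be informative with 12 patients, although finer scales for both measures are already in the plan

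*Combined protocol and SAP*

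**What the plan says.** Section 2.0, secondary objective 3, is to explore Gli-1 in archived pre-treatment tissue "as a candidate biomarker for efficacy of ribavirin in these cancers". The one analysis planned for it, in Section 14.0, asks whether the "anti-Gli-1 IHC score (scale 0-3 dichotomized to low/high) is related to response (CR+PR) using Chi-square or Fisher's exact test".

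Section 14.0 bands the 0-3 score by the percentage of positive tumor cells (cuts at 5%, 30% and 50%). Neither it nor Section 9.2 says which scores count as low and which as high. Progression-free survival, stable versus progressive disease and change in tumor size are not related to Gli-1 anywhere. The undichotomized score is used only to describe baseline and post-progression tissue in responders.

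Finer outcome data are collected. Measurable disease is an entry criterion, lesions are recorded in millimeters, and Section 12.1.2 states: "The baseline sum diameters will be used as reference to further characterize any objective tumor regression in the measurable dimension of the disease". Applying the PR and PD definitions in Section 12.1.4.1 requires that sum at follow-up too.

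**The concern.** Both variables are cut to two levels before being compared, in a trial where "A sample size of 12 patients will be accrued" and few responses are likely. Among non-responders, a patient with 28% shrinkage and one with 19% growth count as the same outcome. That contrast matters for this marker, because Section 3.0 presents Gli-1 as a mechanism of resistance: such a marker should help separate progression from disease control, and CR+PR yes/no pools the two.

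What is at stake is whether objective 3 yields anything usable. A test that is non-significant almost whatever the truth gives little basis for a hypothesis, and a reader could take its result as evidence against Gli-1.

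**Working it through.** **Inputs from Section 14.0.** n = 12. Target response rate 30%, with the probability of "observing 0 or 1 responses out of 12 patients if the true response rate is 30%), is 0.09". Success rule: "radiographic responses are observed in at least 2 of 12 subjects". Head and neck: "historical estimate for objective response rate with palliative chemotherapy after first line is 15" percent. Cervix: "the response rate of palliative single agent chemotherapy for advanced cervical cancer is approximately 15-20" percent. Expected responders: 12 × 0.15 = 1.8; 12 × 0.20 = 2.4; 12 × 0.30 = 3.6.

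**Assumption.** Two-sided 0.05 is used as a yardstick. The plan gives no level for this test.

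**1. The plan's own figure.** P(0 or 1) at 30% = 0.70^12 + 12 × 0.30 × 0.70^11 = 0.014 + 0.071 = 0.085, which rounds to the stated 0.09.

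**2. The same formula at the historical rates.**
- 15%: 0.142 + 0.301 = 0.44
- 20%: 0.069 + 0.206 = 0.27

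With 0 responders there is no comparison. With 1, the smallest possible Fisher p is 1/12 = 0.083 (a 1/11 split).

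**3. Even split (6/6), r responders all in one group.** Two-sided Fisher p = 2 × C(6,r) / C(12,r).

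| r | p |
|---|---|
| 2 | 2 × 15/66 = 0.455 |
| 3 | 2 × 20/220 = 0.182 |
| 4 | 2 × 15/495 = 0.061 |
| 5 | 2 × 6/792 = 0.015 |

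So at least 5 responders are needed. P(4 or fewer) is 0.98 at 15%, 0.93 at 20% and 0.72 at 30%.

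**4. Uneven splits, best possible separation.**
- 2 responders, both in the smaller group: 2/10 gives 1/66 = 0.015; 3/9 gives 3/66 = 0.045; 4/8 gives 6/66 = 0.091; 5/7 gives 10/66 = 0.152.
- 3 responders: 2/10 (two in the smaller group) 10/220 = 0.045; 3/9 1/220 = 0.005; 4/8 4/220 = 0.018; 5/7 10/220 = 0.045.
- 4 responders: 3/9 (three in the smaller group) 9/495 = 0.018; 4/8 1/495 = 0.002; 5/7 5/495 = 0.010.

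Significance is therefore possible with 2 to 4 responders, but only in these near-perfect configurations.

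**5. Chi-square is no way out.** With 4 or fewer responders, at least one expected cell count is always below 5 (at most 4 × 11/12 = 3.7 in a responder cell). Three responders against none at 6/6 gives an uncorrected chi-square p of 0.046 where Fisher gives 0.18.

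**6. Illustrative gain from the finer scales.** Simulation with n = 12, an assumed latent correlation of 0.6 between Gli-1 and tumor change, bivariate normality, and the four score levels used equally. Chance of p ≤ 0.05:

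| Analysis | 15% response | 20% | 30% |
|---|---|---|---|
| Fisher, cut at the population median | 3% | 6% | 9-10% |
| Fisher, exact 6/6 split | 0.4% | 1% | 3-3.5% |
| Spearman, 0-3 score by % change | 46% | 47% | 47% |
| Spearman, both continuous | 50% | 50% | 49% |

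With the 0-3 score, Spearman stays near 45% if the patients with most growth are tied at worst rank. It falls to about 18% if each patient has a 25% chance of worst rank unrelated to Gli-1. At a correlation of 0.5 with complete data it is about 33%.

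**The case against.** The strongest reply is that the plan never claims more than exploration. Objective 3 says explore, Section 14.0 labels the tissue work hypothesis generation and the scoring provisional, and it gives no significance level or power for Gli-1. CR+PR is the trial's own efficacy measure, so relating the marker to it is coherent, and 12 patients can be listed individually. This stands to the extent that no stated power is contradicted. It does not excuse discarding information already collected: an exploratory aim is better served by the full scales.

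A reader might infer three stronger things that the documents do not support.

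- **That objective 3 cannot be answered.** The plan uses fixed bands and names no median cut, so uneven splits are possible, and step 4 shows that some reach 0.05.
- **That the table will usually be empty.** The chance of no responder is 14% at 15%, 7% at 20% and 1.4% at 30%.
- **That raw staining percentages are certain to be available.** The bands are defined by percentage, but only the 0-3 score is certain to be recorded.

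The gain is also conditional. The 0.6 correlation has no source in the documents. The first on-treatment scan falls in the last week of cycle 2 (Section 9.1), so some patients may leave without one, and worst-ranking them can cost most of the advantage.

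**Conclusion.** The point holds as an avoidable loss of information. It is neither an error against a stated power nor a proof that the objective is unanswerable. At 1.8 to 3.6 expected responders, the planned 2x2 test is very unlikely to be informative: the chance that Fisher cannot reach 0.05 at any split is 44%, 27% and 8.5% at response rates of 15%, 20% and 30%. Beyond that, success needs either 5 or more responders at an even split or near-perfect separation at an uneven one.

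The responder range is derived from the plan's rates; the plan itself states no expected count. The exact results rest on the 0.05 yardstick. The comparison of roughly 0.4-10% with 45-50% rests further on the assumed correlation, normality and near-complete scans, with about 18% as the less favorable case shown.

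**What to change.** In Section 14.0, add as the main exploratory analysis for objective 3:

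- The Spearman correlation, with a confidence interval, between the ordered 0-3 Gli-1 score (or the percentage of positive cells, if recorded) and best percentage change from baseline in the sum of target-lesion diameters.
- A waterfall plot marked by Gli-1 score.
- A missing-data rule: rank patients who progress by new lesions, or who have no follow-up scan, as worst. Repeat the analysis without the patients who have no scan.
- The low/high by CR+PR table kept as descriptive only, with its cut-point stated.

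The cost is a few lines of text. No new tissue, scans or visits are needed, and the primary endpoint is untouched. The downside is that the result depends on the worst-rank rule and remains imprecise. For example, an observed correlation of 0.6 in 12 patients would have an approximate 95% interval of tanh(0.693 ± 1.96 × 1/√9), or 0.04 to 0.87, and somewhat wider with ties.
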